8.3.1. Adverse Events

Adverse events will be monitored from the time the participant signs the ICF until at least 28 days after the last dose of study drug. Immune-related AEs will be collected until 90 days after the last dose of study drug. Adverse events that begin or worsen after informed consent should be recorded on the Adverse Events Form in the eCRF regardless of the assumption of a causal relationship with the study drug. Conditions that were already present at the time of informed consent should be recorded on the Medical History Form in the eCRF. Adverse events (including laboratory abnormalities that constitute AEs) should be described using a diagnosis whenever possible rather than by individual underlying signs and symptoms.

Adverse events will be reported by the participant (or, when appropriate, by a caregiver, surrogate, or the participant's legally authorized representative). The investigator and any qualified designees are responsible for detecting, documenting, and recording events that meet the definition of an AE or SAE and remain responsible for following-up on AEs that are serious, considered related to the study treatment/procedures, or that caused the participant to discontinue the study treatment. Care will be taken not to introduce bias when detecting AEs and/or SAEs. Open-ended and nonleading verbal questioning of the participant, such as "How are you feeling?" is the preferred method to inquire about AE occurrences. Adverse events may also be detected when they are volunteered by the participant during the screening process or between visits, or through physical examinations, laboratory tests, or other assessments. The definition, reporting, and recording requirements for AEs are described in Section [9](#).

All SAEs will be recorded and reported to the sponsor or designee within 24 hours. The investigator will submit any updated SAE data to the sponsor within 24 hours of it being available.

After the initial AE/SAE report, the investigator is required to proactively follow each participant at subsequent visits/contacts. All SAEs, and nonserious AESIs (as defined in Section 9.5), will be followed until resolution, stabilization, the event is otherwise explained, or the participant is lost to follow-up (as defined in Section 7.3).

8.3.2. Forced Expiratory Volume Test

Participants with known or suspected COPD or asthma must have an FEV1 test during screening. See Section 6.5.1.2 for details on participants with higher risk of respiratory complications.

8.3.3. Physical Examinations

Physical examinations must be performed by a medically qualified individual, such as a licensed physician, physician's assistant, or an advanced registered nurse practitioner, as local law permits. Abnormalities identified after the first dose of study drug constitute an AE if they are considered clinically meaningful, induce clinical signs or symptoms, require concomitant therapy, or require changes in study drug. Investigators should pay special attention to clinical signs related to previous serious illnesses.

8.3.3.1. Comprehensive Physical Examination

At the screening visit, a comprehensive physical examination should be conducted. The comprehensive physical examination will include height and body weight, and assessment(s) of the following organ or body systems: skin; head, eyes, ears, nose, and throat; thyroid; lungs; cardiovascular system; abdomen (liver, spleen); extremities; and lymph nodes; as well as a brief neurological examination.

8.3.3.2. Targeted Physical Examination

The targeted physical examination will be a symptom-directed evaluation. The targeted physical examination will include body weight and assessment(s) of the body systems or organs, as indicated by participant symptoms, AEs, or other findings.

8.3.4. Vital Signs

Vital sign measurements (to be taken before blood collection for laboratory tests), include blood pressure, pulse, respiratory rate, body temperature. Blood pressure and pulse will be taken with the participant in the recumbent, semirecumbent, or sitting position after 5 minutes of rest. Weight will also be assessed at each study visit. Abnormal vital sign results identified after the first dose of study treatment constitute an AE if they are considered clinically meaningful, induce clinical signs or symptoms, require concomitant therapy, or require changes in study drug.

8.3.5. Electrocardiograms

Electrocardiograms (triplicate 12-lead ECGs) will be obtained using an ECG machine that automatically calculates the heart rate and measures PR, QRS, QT, and QTc intervals. All

12-lead ECGs will be performed in triplicate (within approximately 15 minutes) with the participant in a recumbent or semirecumbent position after 5 minutes of rest. Whenever possible, ECGs should be performed immediately before chemistry [REDACTED] assessments.

The 12-lead ECGs will be interpreted by the investigator at the site to be used for immediate participant management. Additional 12-lead ECGs may be performed as clinically indicated to manage participant safety. The decision to include or exclude a participant or withdraw a participant from the study treatment based on an ECG flagged as "Abnormal, Clinically Significant" is the responsibility of the investigator, in consultation with the sponsor's medical monitor, as appropriate. Clinically notable abnormalities that are considered clinically significant in the judgment of the investigator are to be reported as AEs.

8.3.6. Eastern Cooperative Oncology Group Performance Status

Eastern Cooperative Oncology Group performance status will be used to evaluate the effect of the disease status on the activities of daily living according to the criteria in [Table 21](#). When scheduled, ECOG performance status assessments should be obtained before any other study procedures planned for the same day whenever possible.

Table 21: ECOG Performance Status

Grade	Performance Status
0	Fully active, able to carry on all pre-disease performance without restriction.
1	Restricted in physically strenuous activity but ambulatory and able to carry out work of a light or sedentary nature, eg, light house work, office work.
2	Ambulatory and capable of all self-care but unable to carry out any work activities. Up and about more than 50% of waking hours.
3	Capable of only limited self-care, confined to bed or chair more than 50% of waking hours.
4	Completely disabled. Cannot carry on any self-care. Totally confined to bed or chair.
5	Dead.

Source: [Oken et al 1982](#).

8.3.7. Laboratory Assessments

See [Table 22](#) for the list of clinical laboratory tests to be performed and the Schedule of Laboratory Assessments (see [Table 5](#) and [Table 6](#)) for the timing and frequency. A certified laboratory local to the investigative site will perform most of the clinical laboratory assessments for safety (ie, blood chemistries, hematology assessments, lipid panel, thyroid panel, and urinalysis). All local laboratory assessments should be performed using standard procedures on the days indicated in [Table 5](#) and [Table 6](#). [Table 22](#) lists the specific laboratory analytes required for each test. Some additional tests (ie, [REDACTED] urinary orotic acid; see [Table 23](#)) will be conducted by 1 or more central laboratories, on the days indicated in [Table 5](#) and [Table 6](#). The investigative site will enter the laboratory results and laboratory normal ranges into the eCRF. Additional testing may be required by the sponsor based on emerging safety data. Additional tests may also be performed if clinically indicated.

Clinically significant abnormal laboratory findings are those that are not associated with the underlying disease, unless judged by the investigator to be more severe than expected for the participant's condition. All laboratory tests with values considered clinically significantly abnormal during participation in the study or within 30 days after the last dose of study treatment (or until start if a new anticancer therapy) should be repeated until the values return to normal or baseline or are no longer considered clinically significant by the investigator or medical monitor.

Screening laboratory assessments must be performed within 7 days of Cycle 1 Day 1. If performed more than 7 days before Cycle 1 Day 1, then the tests must be repeated and eligibility confirmed before study treatment administration on Cycle 1 Day 1. Laboratory samples collected on study Day 1 must be performed before study treatment administration. After Cycle 1, predose laboratory procedures can be conducted up to 72 hours before study treatment administration (within the study windows indicated in [Table 3](#) and [Table 4](#); [Table 5](#) and [Table 6](#); see [Table 7](#) for the SoA for all participants as of Protocol Amendment 3), and results should be reviewed by the investigator or qualified designee and found to be acceptable before a new cycle of treatment is initiated.

NOTE: As of Protocol Amendment 3, laboratory assessments should be performed in accordance with the standard of care of the investigational site for the participant's condition. Laboratory results do not need to be reported in the eCRF, but all laboratory results corresponding with an SAE or an AESI will be reported on the SAE form. In addition, pregnancy testing will continue to be performed for all participants as per the SoA in [Table 7](#).

Table 22: Required Laboratory Analytes

Chemistries	Hematology	Urinalysis With Microscopic Examination	Serology ^a
Albumin	Complete blood count, including:	Color and appearance	Hepatitis B surface antigen
Alkaline phosphatase	
 • Hemoglobin • Hematocrit • Platelet count • Red blood cell count • White blood cell count 	pH and specific gravity	Hepatitis B surface antigen antibody
ALT		Bilirubin	Hepatitis B core antibody
Ammonia		Glucose	HBV DNA
Amylase		Ketones	HCV antibody
██████████		Leukocytes	HCV RNA
AST		Nitrite	HIV RNA (if required by local regulations)
Bicarbonate or CO ₂	Differential count, including:	Occult blood	
BUN or urea	
 • Basophils • Eosinophils • Lymphocytes • Monocytes • Neutrophils 	Orotic acid ^b	
Calcium		Protein	
Chloride			
Creatinine			
Glucose			
Lactate dehydrogenase	Absolute values must be provided for:		
Lipase	
 • WBC differential laboratory results 		
██████████	
 • Blood type test^c 		
Phosphate			
Potassium			
Sodium			
Total bilirubin			
Direct bilirubin (if total bilirubin is elevated above ULN)			
Total protein			
Uric acid			
Lipid Panel		Pregnancy Testing	
		Total cholesterol	Female participants of childbearing potential require a serum pregnancy test at screening and a urine pregnancy test on Day 1 of every cycle, at EOT, and as medically indicated or per country or institutional requirements.
		Triglycerides	
		LDL	
		HDL	
Thyroid panel		Pregnancy tests (serum or urine) should be repeated if required by local regulations.	
		TSH	
		FT4	
		FT3/T3	

Note: Additional tests may be required, as agreed upon by the investigator and sponsor, based on emerging safety data.

^a Hepatitis B and C viral loads by PCR assay only need to be assessed when respective serology results are positive. Hepatitis B virus DNA does not need to be performed if the surface antibody is the only positive result.

^c For participants receiving daratumumab SC (monotherapy or in combination with INCB001158) only.

8.3.7.1. Blood Type Assessment

A blood type test will be performed as outlined in [Table 22](#). CD38 is expressed on erythrocytes to a minor extent. Hemolysis could occur after the administration of daratumumab SC, which would confound the blood type assessment. To be cautious and in case of urgent need for blood transfusion, the participant's blood type will be assessed before administration of daratumumab SC, and it is recommended that the participants carries a card with the blood type during the study at all times.

8.3.7.2. Chemistries

See [Table 5](#) and [Table 6](#) for sampling time points and the Laboratory Manual for details of how to process, store, and ship the samples to the certified central laboratory or laboratories for sample analysis.

8.3.7.3. Urinalysis

Standard urinalysis will be performed as outlined in [Table 22](#), and urinary orotic acid, which is a marker of urea cycle inhibition that is a potential side effect of INCB001158 (refer to the [IB](#)), will be assessed as outlined in [Table 23](#). Participants must fast at least 8 hours before each clinic visit and void their bladder in the morning before providing the predose urine sample at the clinic.

Table 23: Sample Collection Times for Assessments of Urinary Orotic Acid

Study Visit	Time
C1D1	Predose and 6 h (\pm 1 h) postdose
C1D8 ^a	Predose
C1D15	Predose and 6 h (\pm 1 h) postdose
C2D1 and D1 of all subsequent cycles	Predose

Note: Additional samples may be collected as clinically indicated.

^a The C1D8 sample will be collected only for participants enrolled in Phase 1.

8.3.7.4. Plasma Ammonia

Plasma ammonia levels are to be tested during screening (see [Table 5](#) and [Table 6](#)). If above the ULN, repeat the sample to confirm the value. If the participant experiences an elevation in urine orotic acid ($> 10 \times$ ULN fasted or $> 40 \times$ ULN of any value) while on study treatment or during the follow-up period, monitor plasma ammonia levels each time the urine orotic acid is tested, at least until orotic acid levels have returned to normal, at the investigator's and medical monitor's discretion.

8.3.7.5. Pregnancy Testing

A serum pregnancy test will be required for all women of childbearing potential during screening. Urine pregnancy tests will be performed locally as outlined in [Table 5](#) and [Table 6](#), as medically indicated (eg, in case of loss of menstrual cycle, when pregnancy is suspected), or per country-specific requirement (note that country-required urine pregnancy testing will be outlined and communicated to investigational sites under separate cover). If a urine pregnancy test is positive, the results should be confirmed with a serum pregnancy test.

If the serum pregnancy test is negative after a urine test was positive, the investigator will assess the potential benefit/risk to the participant and determine whether it is in the participant's best interest to resume study treatment and continue participation in the study.

[figure not shown]
If a pregnancy is confirmed by a serum pregnancy test, see Section [9.7](#) for reporting requirements.

8.3.7.6. Serology

Hepatitis and HIV screening assessments will be performed at the screening visit (see [Table 5](#)) to rule out hepatitis and HIV infection, respectively; required analytes are shown in [Table 22](#).

Participants who are positive for anti-HBs or anti-HBc will undergo testing for HBV DNA by PCR as specified in [Table 5](#) and [Table 6](#). Participants with serologic findings suggestive of HBV vaccination (anti-HBs positivity as the only serologic marker) AND a known history of prior HBV vaccination do not need to be tested for HBV DNA by PCR.

Generally, hepatitis and HIV tests should be performed early in the screening process due to the length of time needed to obtain the results. Additional tests may be performed if clinically indicated.

8.6. Unscheduled Visits

Unscheduled study visits may occur at any time if medically warranted. Any assessments performed at those visits should be recorded in the eCRF.

8.7. End of Treatment and/or Early Termination

When the participant permanently discontinues all study treatment, whether the participant is terminating the study early or the participant has completed the study, the EOT visit should be conducted. If the EOT visit coincides with a regular study visit, the EOT evaluations will supersede those of that scheduled visit, and the data should be entered in the EOT visit in the eCRF. The participant should be encouraged to return for the follow-up visit.

8.8. Follow-Up

8.8.1. Safety Follow-Up

The safety follow-up period is the interval between the EOT visit and the scheduled follow-up visit, which should occur 28 to 35 days after the EOT visit (or after the last dose of study treatment if the EOT visit was not performed). Adverse events and SAEs must be reported up

until 1) at least 28 days after the last dose of study treatment and 90 days for irAEs or the start of a new anticancer therapy or 2) until toxicities resolve, return to baseline, or are deemed irreversible, whichever is longer. Reasonable efforts should be made to have the participant return for the follow-up visit and report any AEs that may occur during this period. If the participant cannot return to the site for the safety follow-up visit, the participant should be contacted by telephone for assessment of AEs and SAEs, and this contact should be documented in the source.

If a participant is scheduled to begin a new anticancer therapy before the end of the 28- to 35-day safety follow-up period, the safety follow-up visit should be performed before a new anticancer therapy is started. Once a new anticancer therapy has been initiated, the participant will move into the survival follow-up period.

NOTE: As of Protocol Amendment 3, data will only be collected for SAEs, AESIs, and pregnancy. Once a new anticancer therapy has been initiated, the participant will no longer be followed for survival follow-up beyond the last safety follow-up visit.

8.8.2. Disease Status Follow-Up

Participants who discontinue study treatment for a reason other than disease progression will move into the disease status follow-up period and should be assessed every 8 weeks \pm 7 days after EOT to monitor disease status. Every effort should be made to collect information regarding disease status until:

- The start of new anticancer therapy.
- Disease progression.
- Death.
- The end of the study.

NOTE: As of Protocol Amendment 3, disease status follow-up visits for participants who discontinue study treatment for a reason other than disease progression are no longer required beyond the safety follow-up visit. The last disease status follow-up data will be recorded in the eCRF at the time of the safety follow-up visit. The last study visit will be the safety follow-up visit.

8.8.3. Survival Follow-Up

Once a participant has received the last dose of study drug, has confirmed disease progression, or starts a new anticancer therapy, the participant moves into the survival follow-up period and should be contacted by telephone, email, or visit at least every 12 weeks following EOT to assess for survival status until death, withdrawal of consent, or the end of the study, whichever occurs first.

For participants having entered the survival follow-up period of the study, the site will use continuing participant records to supply data on subsequent treatment regimens, disease assessments (if discontinued treatment for a reason other than progression), and OS in the eCRF. For participants who do not intend to return to the study investigator for their ongoing care, follow-up should be maintained by phone contact, patient records, and public records/databases at intervals of no longer than 12 weeks.

NOTE: As of Protocol Amendment 3, the survival follow-up visits for participants who discontinue study treatment for a reason other than disease progression are no longer required beyond the safety follow-up visit. The last survival follow-up data will be recorded in the eCRF at the time of the safety follow-up visit. The last study visit will be the safety follow-up visit.

9. ADVERSE EVENTS: DEFINITIONS AND PROCEDURES FOR RECORDING, EVALUATING, FOLLOW-UP, AND REPORTING

NOTE: As of Protocol Amendment 3, the only safety data that will be collected will be related to SAEs, AESIs, and pregnancy. The safety follow-up visits may be completed remotely (such as by televisit).

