6.7.2. Criteria and Procedures for Dose Interruptions and Adjustments of Study Drug

Safety concerns should be discussed with the sponsor immediately upon occurrence or awareness to determine if the participant should continue or discontinue study treatment.

As described in Section 2.3, INCB001158 has the potential to cause toxicity related to the inhibition of arginase 1 in the hepatic urea cycle. [Table 17](#) provides guidance for INCB001158 dose modifications and participant management if there is evidence of urea cycle inhibition.

Dose modification and toxicity management for potential irAEs associated with INCB001158 should be managed as follows.

Adverse events (both nonserious and serious) associated with INCB001158 exposure may represent an immunologic etiology. These irAEs may occur shortly after the first dose or several months after the last dose of treatment and may affect more than 1 body system simultaneously. Therefore, early recognition and initiation of treatment is critical to reduce complications. For suspected irAEs, ensure adequate evaluation to confirm etiology or exclude other causes. Additional procedures or tests such as bronchoscopy, endoscopy, or skin biopsy may be included as part of the evaluation. Based on the severity of irAEs, withhold or permanently discontinue INCB001158 and administer corticosteroids.

[Table 17](#) summarizes the AE dose modification actions for INCB001158. Of note, when indicated by [Table 17](#) to mitigate irAEs, the dose of INCB001158 must be reduced using the dosing levels outlined in [Table 11](#). Once reduced, re-escalation of INCB001158 is not permitted.

Table 17: Guidelines for Interruption and Restarting of Study Drug

Adverse Event	Toxicity Grade or Conditions (CTCAE v5)	Action Taken	AE Management With Corticosteroid and/or Other Therapies	Monitor and Follow-Up
Evidence of urea cycle inhibition	
 Fasting urinary orotic acid $> 2 \times$ and $\leq 10 \times$ ULN Any urinary orotic acid $> 2 \times$ and $\leq 40 \times$ ULN 	
 Continue. 	
 None. 	
 Retest 1 week later. If still abnormal, withhold INCB001158 and retest every week until orotic acid returns to normal level, then consider restarting (at a lower dose) in consultation with medical monitor.

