9.4. Reporting of Serious Adverse Events

Regardless of suspected causality (eg, relationship to study treatment, or study procedure[s]), all SAEs occurring after the participant has signed the ICF through 28 days after the last dose of study drug *or* until the participant starts a new anticancer therapy, whichever occurs earlier) must be reported to the sponsor (or designee) within **24 hours** of learning of its occurrence, unless otherwise specified by the Protocol. Serious AEs that are irAEs must be reported until 90 days after the last dose of study drug. The investigator will submit any updated SAE data to the sponsor (or designee) within 24 hours of it being available.

Investigators are not obligated to actively seek AE or SAE information after conclusion of the study participation. If the investigator learns of any SAE, including death, at any time during this period, and he/she considers the event to be reasonably related to the study treatment or study participation, the investigator must notify the sponsor (or designee) within 24 hours of becoming aware of the event.

After the initial AE/SAE report, the investigator is required to proactively follow each participant at subsequent visits/contacts. All SAEs, and nonserious AESIs (as defined in Section 9.5), will be followed until resolution, stabilization, the event is otherwise explained, or the participant is lost to follow-up (as defined in Section 7.3).

Prompt notification by the investigator to the sponsor of a SAE is essential so that legal obligations and ethical responsibilities towards the safety of participants and the safety of a study treatment under clinical investigation are met.

If the SAE is not documented in the Reference Safety Information in the respective INCB001158 and daratumumab IBs, or Darzalex/Darzalex FASPRO Product Information (new occurrence) and is thought to be related to the sponsor's study drug, the sponsor or its designee may urgently require further information from the investigator for expedited reporting to health authorities.

The sponsor or its designee may need to issue an Investigator Notification to inform all investigators involved in any study with the same drug that this SAE has been reported. Suspected unexpected serious adverse reactions will be collected and reported to the competent authorities and relevant ethics committees in accordance with Directive 2001/20/EC, or as per national regulatory requirements in participating countries.

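### Immune-related AEs are to be collected to 90 days after the last dose, but no AE assessment is scheduled after the safety visit 28 to 35 days after end of treatment

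*Protocol*

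**What the plan says.** **The duty.** Protocol 8.3.1: "Immune-related AEs will be collected until 90 days after the last dose of study drug". Protocol 9.4: "Serious AEs that are irAEs must be reported until 90 days after the last dose of study drug". Protocol 8.8.1 sets the reporting period at "at least 28 days after the last dose of study treatment and 90 days for irAEs". Section 6.6.3 uses the same 90 days for irAEs when a participant stops treatment after a DLT. Section 6.7.2 gives a reason for a long window: "These irAEs may occur shortly after the first dose or several months after the last dose of treatment". Amendment 3 does not withdraw any of this. Section 9.5 classes potentially immune-related events as AESIs, and its Amendment 3 note keeps AESIs reportable in the eCRF.

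**The schedule.** Table 7 is the only schedule of activities from Amendment 3 on. It has three columns: treatment, EOT and safety follow-up. Section 8.8.1 places the safety visit at a time "which should occur 28 to 35 days after the EOT visit", or after the last dose if there was no EOT visit. The notes in 4.2 and 7.1.2 end disease-status and survival follow-up beyond that visit. Sections 8.8.2 and 8.8.3 add: "The last study visit will be the safety follow-up visit". Those last two notes are worded for participants who stop for a reason other than progression, but 4.2, 7.1.2 and Table 7 carry no such limit.

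**After participation ends.** Protocol 9.4: "Investigators are not obligated to actively seek AE or SAE information after conclusion of the study participation".

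**The concern.** The collection period and the visit schedule do not fit together. A new irAE with onset on day 60 after the last dose falls inside the period that 8.3.1 requires, but nothing in Table 7 would prompt anyone to look for it. Under 4.2 a participant completes the study at the last procedure in the schedule, which is now the safety visit, and from there 9.4 releases the investigator from active enquiry.

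This matters more here than in most trials that close early. Section 2.3 names immune-related AEs among the three main toxicity risks of INCB001158. The SAP (sections 2.2, 3, 9 and 10.1) drops the efficacy analyses, so safety is what remains. SAP 8.2.3 and 8.2.4 count participants with any irAE, and the TEAE definition in SAP 8.2.1 has no end date. Nothing in the SAP tells the reader how far after the last dose irAEs were actively sought.

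**Working it through.** The plan states no figure for coverage of the window, so there is none to reproduce. The check is a day count.

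**Inputs**
- Window: 90 days after the last dose of study drug (8.3.1, 9.4). Study drug means INCB001158 only (6.1).
- EOT window: +7 days (Table 7). The table does not say from what. I assume EOT falls 0 to 7 days after the last INCB001158 dose.
- Safety visit: 28 to 35 days after EOT (Table 7, 8.8.1).

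**Formula:** days without scheduled contact = 90 − (lag from last dose to EOT + days from EOT to safety visit).

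| Lag to EOT | Visit after EOT | Day of last contact | Days left | Share of 90 |
|---|---|---|---|---|
| 0 | 28 | 28 | 62 | 68.9% |
| 0 | 35 | 35 | 55 | 61.1% |
| 7 | 28 | 35 | 55 | 61.1% |
| 7 | 35 | 42 | 48 | 53.3% |

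**Sensitivity to the lag.** Half the window is 45 days. The gap falls to half or less once the lag reaches 45 − 35 = 10 days (visit at EOT + 35) or 45 − 28 = 17 days (visit at EOT + 28). It closes at 90 − 35 = 55 or 90 − 28 = 62 days. Longer lags can arise because daratumumab may continue while INCB001158 is held or stopped (6.7.1), and EOT comes only when all study treatment has stopped (8.7). Taking hold lengths that the protocol mentions:
- 28 days (6.7.1): 27 to 34 days left, 30% to 38%.
- 42 days (the 6 weeks in 7.1.1): 13 to 20 days left, 14% to 22%.
- 84 days (the 12 weeks in Table 17): none left.

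**What Amendment 3 changed.** In Table 3, as extracted, the AE-assessment row has ten marks: screening, seven treatment visits, EOT and the safety visit. None falls under disease status or survival. The absence of a later AE assessment therefore predates the amendment. What the amendment removed were other contacts in or near the window. With EOT on day 0 to 7, the 8-weekly disease-status contact fell on day 0 + 56 − 7 = 49 to 7 + 56 + 7 = 70. The 12-weekly survival contact fell on day 0 + 84 − 7 = 77 to 7 + 84 + 7 = 98.

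**When the period ends.** The passages also differ here. Section 8.8.1 has "90 days for irAEs or the start of a new anticancer therapy" and counts from study treatment. Section 8.3.1 and the serious-irAE sentence in 9.4 count from study drug and have no new-therapy exception.

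**The case against.** The best defence is that 90 days is a reporting period, not a visit, and reporting needs no appointment. Several routes stay open:
- AESIs remain reportable in the eCRF (9.5).
- Unscheduled visits are allowed when medically warranted (8.6).
- Known study-drug toxicities are followed to resolution, even past the follow-up visit (7.1.2).
- Related SAEs that the investigator learns of must still be notified within 24 hours (9.4).

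This stands in part. A reader might infer that the 90-day requirement cannot be met, or that participants have no contact at all. The documents do not support either reading. What is missing is scheduled contact. The remaining routes are passive or serve events already known, so none is set up to detect a new irAE.

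A reader might also infer that Amendment 3 created the gap. Table 3 shows otherwise, and the contacts that were removed were for disease and survival status, not AEs. The 8-weekly one applied only to participants who stopped without progression, and the 12-weekly one could fall after day 90.

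Finally, enrollment had ended, and the Amendment 3 rationale says that enough data had been collected for the safety analysis. Only participants still on study are affected. The documents do not give their number, so the effect on the irAE count cannot be sized.

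**Conclusion.** The mismatch is real and should be reconciled. A 90-day irAE duty survives Amendment 3, while the schedule supports active ascertainment only to the safety visit. With EOT 0 to 7 days after the last INCB001158 dose, 48 to 62 of 90 days (53% to 69%) rest on spontaneous reporting.

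That range depends on the assumed anchor for the EOT window and describes the case where INCB001158 runs up to EOT. It should not be read as applying to every participant: the gap is smaller or absent after a long INCB001158 hold or early stop, and 8.8.1 can be read as closing the period when new anticancer therapy begins.

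Nor should one conclude that the SAP misreports a 90-day incidence. It makes no such claim; it states no ascertainment limit, and a reader who has the protocol could supply 90 days.

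**What to change.** Reconcile the passages in one of two ways.

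1. **Keep 90 days and schedule for it.** Add to Table 7 one remote irAE contact at about day 90 after the last INCB001158 dose, for remaining participants who received INCB001158. The Amendment 3 note at the head of section 9 already allows remote safety visits. The 4.2, 7.1.2, 8.8.2 and 8.8.3 notes would need to allow for this contact. Cost: one call per participant and a slightly later last-participant-out.
2. **Align the window with the schedule.** Change the irAE period in 6.6.3, 8.3.1, 8.8.1 and 9.4 to end at the safety visit, and state in SAP 8.2.3 and 8.2.4 that irAE counts are actively ascertained only to that visit. Cost: wording only, but late-onset events of the kind 6.7.2 anticipates would then fall outside the stated collection period.

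Under either option, use one anchor (study drug or study treatment) and say whether new anticancer therapy ends the irAE period.
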